A Test of the Safety, Effectiveness, and Acceptability of an Improvised Dressing for Sickle Cell Leg Ulcers in a Tropical Climate

NCT04479618

As of June 3, 2021

IV. Project Proposal

1. Introduction:

a. Review of Literature

Sickle Cell Leg Ulcers:

One in 300 Jamaicans have the most serious form of sickle cell disease (HgbSS), and of these, between 30% and 70% will suffer from sickle cell leg ulcers (SCLUs).^{1-4,10} Although leg ulcers can affect any age group, by far the majority of sufferers develop their first SCLUs when they are between the ages of 10 and 19.^{2,18}

The SCLUs occur in a younger population, so comorbid conditions such as hypertension, diabetes, peripheral arterial or venous disease, and congestive heart failure are uncommon.¹⁶

SCLUs are found most often along the malleoli, followed by the shins.^{8,10} SCLUs heal 16 times slower than notoriously difficult to heal venous leg ulcers, and in some patients, they never heal, even with decades of expert wound management.^{3,5–7,16} SCLUs often enlarge during the first four weeks of management, and when they do close, they have a higher incidence of recurrence.^{8,16}

SCLUs have an even more negative impact on patient physical quality of life when compared to a myocardial infarction, kidney dialysis, or diabetic foot ulcer.¹⁷ Pain is unrelated to SCLU size and required high doses of opioid, which does not always provide adequate control.^{3,9,11,15,18,19} Because SCLUs often compromise education and employment opportunities, improving wound care for this population benefits the entire community in which they live.^{9–11}

Singh and Minniti, and Clare, Serjeant, et al., defined chronic SCLUs as those with greater than one month duration.^{3,20} Factors affecting the formation and healing of SCLUs or progression to a chronic condition remains elusive.²¹ The correlation with poverty, high serum lactate dehydrogenase, and lower leg venous system damage with SCLUs has been reported.^{3,7,10,18,20} Higher base line hemoglobin levels offer a protection against SCLUs.³ Slough, which is a byproduct of inflammation, is a hallmark of these chronic wounds.^{4,22} Compression therapy and bedrest improve healing of SCLUs, just as they improve the healing of venous ulcers not associated with sickle cell disease.^{3,15,18}

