(3) Is the *improvised dressing* culturally acceptable to health care providers, patients, and families for managing SCLUs in Jamaica?

The expected study outcome is improvised dressing superior effectiveness and quality of life, when compared with usual practice, without increased safety and acceptability issues.^{13,59,60,62} The improvised dressing is likely to be the least expensive choice, with the added benefit of being available as first aid treatment throughout Jamaica. The advanced dressing is likely to be more expensive with respect to materials costs, although fewer dressing changes are anticipated and pain medication expenses are likely to be reduced. Based upon the review of the literature, no serious infections or other safety issues are anticipated for any group. However, to ensure that complications are not overlooked, in addition to the onsite researchers' vigilance, weekly wound photos will be assessed for complications (signs of infection, wound deterioration, or clinically relevant maceration) by two off-site blinded wound experts, Drs. [name] and [name].

Definitions:

Sickle cell leg ulcer – a wound in a HbSS or HbS β^0 positive patient, open greater than one month,⁷ below the level of the knee excluding the plantar surface of the foot.

Closed wound -100% epithelialized with no discernible scab or exudate production (paper napkin remains dry when lightly pressed against area, and no recurrence in the subsequent two weeks)

Safe – infection and other complications (healing-impairing maceration, keloid, and contracture rates) not statistically significantly higher than usual practice, with no major adverse events attributable to the method

Effective – ulcer closure rates or ulcer surface area reduction rates not statistically significantly lower than usual practice

Acceptable – average acceptability scores of 4 or higher on a 1-5 scale

3. Methods and Materials

a. Study design

This study will be a targeted-blinded (the off-site wound experts and the local physicians verifying wound closure and/or complications will be blinded to the randomization group), randomized controlled trial with three arms: (1) usual practice (negative control), (2) the improvised dressing, and (3) the advanced dressing (positive control). The expected outcome is improvised and advanced dressing superiority.

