Decrease in SCLU surface area will be used to answer research question 1. Conducting a power analysis for this study is challenging because only one study of SCLUs has demonstrated a statistically significant outcome, and the effect size was obscured by high standard deviations, which is a common problem in studies of wounds.⁸ Improvised plastic dressings similar to the study dressings were used in 49 chronic pressure ulcers in elderly patients, which are often slow to close, if they heal at all.⁶⁰ These two studies demonstrated a significant difference with confidence intervals of 99% with ~25 patients per group. Based upon these sample sizes and the Central Limit Theorem, it is reasonable to set the minimum sample size for this study at 30 patients per group,.^{88,89}

d. Variables

Dependent Variables (measured weekly - tools and permissions in appendices):

- 1. Persistent wound pain (using the Faces Pain Scale Revised (FPS-R))
- 2. Procedural (dressing change) wound pain
- 3. Amount of pain medication taken, including a total number of morphine equivalents plus non-opioid pain medications
- 4. Approximate time spent standing, or sitting with leg dependent without compression (estimated hours per week)
- 5. Patient overall quality of life (assessed with the ASCQ-Me Emotional, Pain, Social Functioning, Stiffness, and Sleep Impact Short Forms)
- 6. Patient wound-specific quality of life (assessed with the Wound QoL tool)
- 7. Materials costs (estimated, using lowest retail costs on Amazon.com for items not on the UWI price sheets)
- 8. Time spent performing dressing changes
- 9. Wound complication rates (e.g., wound infection, healing impairing maceration, wound deterioration)
- 10. Change in wound surface area (measured in cm² electronically using software that automatically corrects for skew, such as HealthEPix or WoundMatrix)⁹⁰

Dependent Variables (measured one time, at graduation from study)

- 11. Wound closure time, in weeks (see definitions; verified two weeks later. Omit patients whose wounds did not fully close they are included in 10., above.)
- 12. Acceptability of dressing choice patient (5 point Likert scale and qualitative free response)
- 13. Acceptability of dressing choice family member (5 point Likert scale and qualitative free response)
- 14. Acceptability of dressing choice UHWI staff (5 point Likert scale and qualitative free response)

Independent Variables (documented at initial study visit):

1. Patient gender

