As a token of appreciation from the research team and an incentive for patients to return for their study clinic visits, each participant will be presented with a 500JM phone card at the end of each of the three 4-week study periods.

All wound management supplies for all three groups will be donated. Shipping and handling fees will be paid by the Principal Investigator with funds from a Wound Healing Foundation grant. Tallies of supplies used at dressing changes will be priced using the cost of medical supplies purchased by the SCU to determine the estimated cost of the treatment supplies for each patient. The PMD rolls will be valued at \$26.99US.⁹⁸

The Principal Investigator will de-identify the data and compile it from the patient Data Collection Tools onto an Excel spreadsheet. This spreadsheet and the de-identified wound photographs will be backed up onto the Principal Investigator's second password protected hard drive via a secure internet connection at least weekly. Two encrypted USB drives containing the data, including wound photographs, will be updated weekly on an alternating schedule and stored in a securely locked file in [name] office in UWI Department of Surgery.

i. Statistical analysis

A consultant, [name], PhD, Senior Biostatistician at The University of Texas Medical Branch in Galveston, will undertake the analysis.

When all of the patients have completed the study, the remainder of the data from the deidentified Data Collection Tools will be transcribed into an Excel spreadsheet by the Principal Investigator. The data will then be evaluated by the biostatistician using the most recent version of SPSS. Groups will be compared with respect to each of the 14 dependent variables, taking into account any confounding from the 11 independent variables. Results will be reported using descriptive statistics (means, modes, medians, frequencies), student's t test, and ANOVA with 95% CIs, using intent-to-treat.¹³ If the improvised dressing does not attain statistical superiority to usual practice, 80% CIs will be calculated with drop-outs removed from the analyses to evaluate noninferiority.^{13, Appendix: From Oczkowski SJW} Complications will be evaluated both individually and collectively by collapsing the pertinent columns.

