Research questions (1) and (2) will be addressed by using analyses of covariance (ANCOVA) to determine if patients in the improvised dressing group (Group 2) had superior results (95% CI's will fall within *f*, the superiority margins) from usual practice (Group 1) or advanced dressings (Group 3), or, if this is not demonstrated, failed to vary significantly (80% CI's will fall within *f*, the inferiority margins) from usual practice (group 1) or advanced dressings (group 3) with respect to each of the dependent variables, controlling for relevant patient characteristics (the independent variables).

Research question (3) will be addressed with descriptive statistics across Likert items regarding endorsement of and concerns with use of the improvised dressing clinically or in future studies. Qualitative comments will be summarized across providers into content themes. Any differences between nurses, patients, family members, and physicians will also be explored and noted.

All health care providers at UHWI participating in the study will be surveyed to explore their concerns as well as their opinions about each dressing choice, using both qualitative open-ended and a quantitative question on a Likert scale. Results will then be shared with the participating clinical staff to provide them with the evidence concerning each of the three dressing protocols.

j. Data handling and record keeping

All study data will be transferred from written documents to the Principal Investigator's password protected electronic devices, de-identified, and then transmitted over secure internet connections to the backup hard drive in the USA. The paper study documentation and the two encrypted USB drives containing the raw data will be stored in a securely locked file in in [name] office in UWI Department of Surgery for a period of at least two years after the study has been published, after which they may be destroyed.

When all of the patients have completed the study, members of the UHWI research team will proofread the Excel spreadsheet with the de-identified data for transcription errors. This data will then be evaluated by the biostatistician using the most recent version of SPSS.

4. Ethical Considerations

This study will be approved by the Ethics Review Committee (ERC) at UWI and the Jamaican Ministry of Health (MOH) prior to its implementation. It will be listed on clinicaltrials.gov prior to the recruitment of the first study patient.

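### Closure time (variable 11) is compared only among patients whose ulcers closed, so the comparison is not between randomised groups and would usually miss a true closure benefit

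*Combined protocol and SAP*

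**What the plan says.** Section 3d lists 14 dependent variables. Variable 11 is closure time in weeks, recorded when the patient leaves the study, with the rule "Omit patients whose wounds did not fully close they are included in 10., above". The item it points to, variable 10, is change in wound surface area.

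Section 3i applies a between-arm test to the whole list: "Groups will be compared with respect to each of the 14 dependent variables", "taking into account any confounding from the 11 independent variables". The methods named are the t test and "ANOVA with 95% CIs, using intent-to-treat". The same section adds ANCOVA for research questions 1 and 2, "with respect to each of the dependent variables, controlling for relevant patient characteristics".

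Two other statements set the weight of variable 11. Section 3c says "Decrease in SCLU surface area will be used to answer research question 1", so closure time is not the lead measure. The definition of *Effective* in section 2, however, refers to "ulcer closure rates or ulcer surface area reduction rates not statistically significantly lower than usual practice". Closure rate is not one of the 14 variables, and the text available names no method for it.

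The protocol expects incomplete closure. Section 1a says of these ulcers that "in some patients, they never heal, even with decades of expert wound management", and section 3f does not expect every patient's ulcer to close.

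**The concern.** Closing is a post-randomisation outcome that the dressing is meant to influence. Once non-closers are removed, the patients left in each arm have been selected by that outcome, and randomisation no longer makes them comparable. An intent-to-treat label cannot apply to such a comparison. Adjusting for baseline characteristics does not bring the omitted patients back, and keeping them in variable 10 protects the area comparison only.

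There is also a loss of information. If a dressing lets more ulcers close at the same speed, the closers' mean times are equal and the test cannot see the benefit. If the extra closures come late, the better dressing can look slower. At stake is what the trial reports about closure, because variable 11 is the only closure outcome on the list.

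**Working it through.** **The plan's own figure.** Section 3f inflates 90 participants for 25% dropout: 90 / (1 − 0.25) = 120, or 40 per arm recruited and 30 completing. This reproduces. The base of 30 per group cannot be derived, because no effect size, standard deviation or power is given.

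**Inputs.** From the documents: about 30 per arm, three arms, 12 weeks of follow-up, weekly data, 95% confidence intervals (taken as two-sided 5%). Assumed, because the documents give no closure rate or timing: closure by week 12 on usual practice p0 = 10, 20 or 40%; hazard ratio (HR) 2 or 3 for closure; constant hazards; times rounded up to whole weeks.

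**Patients omitted.** With proportional hazards, closure in the better arm is p1 = 1 − (1 − p0)^HR, and the share omitted from the two-arm comparison is 1 − (p0 + p1)/2. For p0 = 20% and HR 2: p1 = 1 − 0.8² = 36%, and the share omitted is 1 − (0.20 + 0.36)/2 = 72%.

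**Chance of a significant result favouring the better dressing** (10,000 simulated trials per row, 30 per arm; 2.5% is expected by chance alone):

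| p0 | HR | p1 | Mean closers | Omitted | t test, closers only | Log-rank, all randomised |
|---|---|---|---|---|---|---|
| 10% | 2 | 19% | 3.0 v 5.7 | 86% | 3% | 17% |
| 20% | 2 | 36% | 6.0 v 10.7 | 72% | 4% | 28% |
| 40% | 2 | 64% | 12.0 v 19.2 | 48% | 6% | 48% |
| 10% | 3 | 27% | 3.0 v 8.1 | 81% | 3% | 40% |
| 20% | 3 | 49% | 6.0 v 14.6 | 66% | 5% | 67% |
| 40% | 3 | 78% | 12.0 v 23.5 | 41% | 12% | 90% |

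In the first row the closers-only figure is 2 to 3%, depending on how trials with too few closers to test are counted. At p0 = 20% the closers' mean times are 6.28 v 6.05 weeks (HR 2) and 6.28 v 5.84 weeks (HR 3), so the benefit barely shows in the means.

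**Dropout.** With 40 per arm, 25% leaving and censoring at the last assessment: 3/4/6% v 18/32/54% (HR 2) and 3/5/14% v 46/73/94% (HR 3).

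**Covariate adjustment.** Three arms of 30, larger ulcers closing more slowly, both methods adjusted for initial area. Closers-only ANCOVA v Cox on all: 3/4/10% v 19/27/44% (HR 2) and 3/7/21% v 42/64/86% (HR 3). The Cox test is slightly liberal at 10% closure (3.7% against 2.5% nominal).

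**More closures at the same speed.** With times uniform over weeks 1–12 and the same p0 and p1, the closers-only test stays at chance (2.1–2.8%) while log-rank reaches 17–85%.

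**Reversal.** With about 6 v 12 closers:

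| Common closures | Extra closures in better arm | Better arm looks slower | Significantly slower |
|---|---|---|---|
| weeks 2–8 | weeks 8–12 | 97% | 36% |
| weeks 1–12 | weeks 8–12 | 84% | 19% |
| weeks 1–12 | weeks 5–12 | 70% | 10% |
| weeks 1–12 | weeks 1–12 | 50% | 2.4% |

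**Other timing.** Lognormal closure times (log-SD 0.3–0.6) are kinder to the closers-only test: 5–6% v 29% at 20% v 36% closure, about 15% v 54–56% at 40% v 64%, and about 40–43% v 94% at 40% v 78%. With constant hazards, an assumed 60% closure on usual practice and HR 3, the figures are 35% v 96%.

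**The case against.** The strongest reply is that little rests on variable 11. Area decrease answers research question 1 and keeps every patient. Closure time among closers is neither of the two criteria in *Effective*, and that definition implies a significance comparison of closure rates, which would catch a dressing that simply closes more ulcers. Section 3i also lists frequencies, so closure counts may appear beside the test and alert a careful reader. All of this stands and limits the reach of the fault. It does not repair the comparison: closure rate is not a listed variable and has no named method in the text available. The protocol refers to appendices that may say more.

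A second reply is that the power figures depend on assumed timing. This also stands. The closers-only test does better with lognormal times and high closure rates, but it stayed below one half, and well below log-rank, in every case tried.

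Third, reversal needs the extra closures to come late. With evenly spread closures or proportional hazards there is no systematic reversal, so it is a possibility and not a prediction.

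Fourth, section 3i need not mean that all 11 covariates enter together. If they did, the closers-only ANCOVA would have 14 parameters for about 14 closers at 10% closure and HR 2, and could not be fitted in 60% of trials. That is one reading only, and the conclusion does not depend on it.

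**Conclusion.** The concern holds. Followed as written, the plan makes a between-arm comparison on patients selected by a post-randomisation outcome and calls it intent-to-treat. That part needs no assumption about closure rates.

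The size does. At 10–40% closure on usual practice, HR 2 or 3, constant hazards and 30 per arm, 41–86% of patients are omitted. The chance of detecting the better dressing is 3–12%, against 17–90% when everyone is analysed. The comparison would therefore usually show no difference for a dressing that truly closes more ulcers.

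The fault is confined to closure time and leaves the area comparison intact. It should be fixed, but it does not threaten the answer on area decrease. The noninferiority fallback with 80% intervals was not assessed, because the text available gives no numerical margin.

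**What to change.** Redefine variable 11 as time from randomisation to verified closure, in all randomised patients and in their randomised arm:

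- Censor patients still open at week 12. Censor those withdrawn or lost at their last closure assessment. Patients moved to usual treatment but still assessed stay in their randomised arm.
- Analyse by Kaplan-Meier and log-rank, with a Cox model adjusted for initial area.
- Once closure is verified, date it at the first weekly visit or photo that showed it. A photo alone cannot meet the dry-napkin criterion. Accept a two-week check made after week 12 for closures first seen in weeks 11–12.
- List the proportion closed by week 12 in all randomised patients (Kaplan-Meier, same censoring) as the closure rate in *Effective*.
- Report closers-only times as description, without a test.
- Add a sensitivity analysis counting withdrawn patients as not closed to week 12, and report withdrawals by arm and reason. Section 3h withdraws patients whose condition has not improved, so censoring may be informative.

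Both withdrawal rules are needed. Assume no true effect, 40 per arm and 40% v 10% withdrawal. If withdrawal is unrelated to healing, counting withdrawn patients as open falsely favours the better-retained arm in 4.5–7.5% of trials (nominal 2.5%), against 1.9–2.5% with censoring. If only non-closers leave, censoring falsely favours the arm with more withdrawals in 4.9–13.1%, against 2.3–2.8% when they are counted as open.

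The cost is mainly wording and some analysis. Weekly photos or visits already supply most of the dates. A late re-check is needed for about 0.5–2 of 30 patients per arm at the assumed rates. Following switched patients for closure to week 12 would be extra work, because section 3h states their treatment but not their assessment. Power for closure remains modest after the change: 17–54% at HR 2.

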Although non-inferiority is an acceptable outcome for the improvised dressing, the review of the literature supports the expectation that it will outperform usual practice. This superiority study design eliminate the motive for the blinded evaluators to minimize differences between groups, biasing the results.¹³ If superiority is attained, the results will be evaluated with intent to treat (ITT) analysis.

If superiority is not demonstrated, the data for the improvised dressing and usual practice dressing will be re-evaluated to assess for noninferiority.¹³ Contrary to superiority trials where use of intention-to-treat is employed to protect against type 1 error, the appropriate approach for noninferiority trials is to use a per-protocol approach,¹³ which, at worst, would exaggerate the differences between treatment groups, thereby yielding a more conservative estimate in the setting of a noninferiority trial.¹³ Thus, only those patients completing treatment in the group to which they were randomized will be retained for any non-inferiority analyses (see appendix for further details).

b. Study population

Individuals diagnosed with sickle cell disease who have a SCLU and reside in the parishes of St. Catherine, St. Andrew, or Kingston parishes of Jamaica and respond to advertisements, recruitment phone calls, or flyers posted at the Sickle Cell Unit (SCU) clinic and UHWI prior to and during the enrollment period will be invited to participate in the study. Members of the UHWI surgical team will call all patients identified by the SCU as having had a SCLU within the past two years to invite them to participate in the study. Jamaican residents who otherwise qualify but who live outside the study area will be included only if they agree to provide their own transportation and faithfully attend all clinic visits.

c. Sample

Study participants must have HbSS or HbS β^0 sickle cell disease, be between the ages of 13 and 70, and have a chronic SCLU, defined as a wound in a patient with sickle cell disease that has been open for at least one month and is below the knee, excluding the plantar surface of the foot. All SCLUs on a single patient will be dressed with the same dressing protocol. The largest ulcer at initial presentation is the study SCLU. If two or more SCLUs in close proximity join into

an enlarged ulcer during the first four weeks of the study, the sum of the initial areas will be considered the initial wound size for calculation purposes.

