- 2. Age of open wound prior to entrance into study (in weeks, patient/family report)
- 3. Previous ulcer treatments (if any)
- 4. Education level (in years)
- 5. Smoking or any use of nicotine (yes/no in past week)^{84,85}
- 6. Mid-arm circumference (a surrogate for nutritional status) 91,92
- 7. Initial area of SCLU in cm^2 (see methods for multiple adjacent SCLUs)
- 8. Initial depth of SCLU at deepest point, in cm
- 9. Anatomic location of SCLU
- 10. ASCQ-Me baseline scores (all measures see appendices)
- 11. Social isolation (lives alone, without nearby support)⁸⁶
- e. Inclusion and exclusion criteria

Inclusion Criteria:

- > Diagnosed with HbSS or HbS β^0 sickle cell disease
- > Ages 13 70 years at study initiation (able to comprehend and give consent)⁸²
- > Males and females, pregnancy is not an issue
- > Open wound below the knee, not including the plantar surface of the foot
- > Wound open for longer than one month (defined as a chronic SCLU)
- > Traumatic, spontaneous, or recurrent SCLU (all etiologies)

Exclusion Criteria:

- > Patient younger than 13 years of age at study initiation
- > Patient older than 70 years of age at study initiation
- Wound open for less than one month by conclusion of study enrollment period (acute wounds could be traumatic wounds unrelated to sickle cell diagnosis)
- ➤ Diagnosis of cancer, hypertension, or chronic renal failure⁸²
- ➤ Diabetes (will screen for undiagnosed diabetes)⁸²
- Active wound infection (evidenced by clinical signs of malodor, dark-colored or thick drainage, or significantly increased warmth at the periwound) which is not resolved by the conclusion of the study enrollment period
- Osteomyelitis (if osteomyelitis is suspected, an ESR will be drawn; > 70mm/h with high platelet levels and low serum albumin warrants a bone biopsy)^{93,94}

> Hydroxyurea use (may be a confound because it reduces inflammation and negates much of the pathology of SSD – may choose to abstain for the study)^{7,95}

f. Sampling

- i. All eligible participants who consent to the study will be included. Participants will be randomized into one of the three groups immediately after the initial cleansing/debridement of their SCLU by the nurse using an electronic random number generator (an app). Waiting until the study dressing is to be applied to generate the random number will provide allocation concealment.

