Patients (and adult relatives of eligible patients under the age of 18) will have the study explained to them by one of the members of the UHWI surgical team. Questions will be addressed thoroughly. Families will be assured that if they choose not to participate in the study, the SCLU will be managed with usual practice. The patient (and a decision-maker of the family, in the case of a minor) must sign the consent for the patient to be enrolled in the study.

Immediately after consent is obtained, the study tools (Patient Data Collection sheet, Faces Pain Scale – Revised (FPS-R), ASCQ-Me, and Wound QoL) will be explained to the patient and family. Baseline persistent pain will be assessed using the Faces Pain Scale – Revised (FPS-R).

All of the initial independent variable data will be handwritten onto the patient's individual Study Data Collection Form upon enrollment in the study. The largest SCLU upon initial presentation is the study wound. All SCLUs will be measured for the first four weekly visits to UHWI. If two or more SCLUs in close proximity join during the first four weeks, the sum of the initial areas will be the initial wound size.

The SCLU(s) will be measured initially by placing two pieces of clear plastic on top of one another and tracing the wound edges. The plastic that came in contact with the wound(s) will be discarded and the plastic with the markings on it will be added to the patient's documentation so that the patient can be shown if the SCLU is becoming smaller at subsequent dressing changes. SCLU area will be measured in cm² electronically from a photo, using software such as HealthEPix or WoundMatrix.

Patients (with the support of their families) will be taught to evaluate and document persistent and dressing change pain, pain medication doses taken, time spent and supplies used at dressing changes, their activity, and their use of compression on a checklist-style Study Continuation Form daily. They will either provide the research team with their weekly summary and wound photo via WhatsApp, or they will attend the clinic weekly so that the research team can obtain this data. Two encrypted USB drives containing the data, including wound photographs, will be updated weekly on an alternating schedule and stored in a securely locked file in the UHWI surgical clinic dressing area, along with the paper study documentation.

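### Materials cost and, on the natural reading, dressing-change time cover all of a patient's ulcers, but the planned size covariate is the study ulcer's area alone; a modest, free gain in precision is missed

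*Combined protocol and SAP*

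**What the plan says.** **What is treated and costed.** Section 3c (Sample) states: "All SCLUs on a single patient will be dressed with the same dressing protocol". Under section 3h (Data collection), patients document daily the "time spent and supplies used at dressing changes", and the supply tallies are priced to "determine the estimated cost of the treatment supplies for each patient". Section 3d lists variable 8 simply as "Time spent performing dressing changes", with no restriction to one ulcer.

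**What is used as the size covariate.** Section 3c says: "The largest ulcer at initial presentation is the study SCLU". Independent variable 7 in section 3d is "Initial area of SCLU in cm^2 (see methods for multiple adjacent SCLUs"). The one exception is in sections 3c and 3h: when neighbouring ulcers join within the first four weeks, "the sum of the initial areas will be the initial wound size". An ulcer that does not merge never enters the covariate.

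**What is available.** Section 3h: "All SCLUs will be measured for the first four weekly visits to UHWI". It also describes measuring the ulcer or ulcers initially.

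**How it is analysed.** Section 3i compares the groups on each of the 14 dependent variables by ANCOVA, drawing on the 11 independent variables. No separate covariate set is given for the patient-level outcomes.

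**The concern.** The outcome and its size covariate are measured on different units. Take a patient with a single 8 cm² ulcer and a patient with four ulcers, the largest 8 cm². Both have the same value of independent variable 7, yet the second needs more material and plausibly more time at each change. The plan's own procedures tie material to ulcer size: in section 3h the plastic is cut slightly larger than the ulcer, and the polymeric membrane dressing extends at least 0.5 cm beyond the wound edges.

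Variation due to the other ulcers goes into the residual. That widens the intervals for cost and time, and a chance difference between arms in the number of ulcers is only partly adjusted for. Both outcomes are named in research question 2 (section 2). Section 3f expects costs to improve significantly, with about 30 patients per group and no power calculation for these outcomes.

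**Working it through.** **1. The plan's own figure.** Section 3f: 90 participants, 25% dropout, up to 120 recruited. 90 / (1 − 0.25) = 120, which reproduces. The 30 per group cannot be derived, because no effect size, SD or power is stated. I use 30 per group and two-sided 0.05 (from the 95% CIs) below.

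**2. Total area in place of largest-ulcer area (closed form).** Let R² be the share of outcome variance explained by total area, and r the correlation of largest with total area. Assume the largest ulcer predicts the outcome only through total area. Residual variance is then 1 − R² with total area and 1 − R²r² with largest area, so

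CI width ratio = √[(1 − R²) / (1 − R²r²)].

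The documents give neither input, so both are assumed:

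| R² | r = 0.98 | r = 0.90 | r = 0.80 |
|---|---|---|---|
| 0.2 | −0.5% | −2.3% | −4.2% |
| 0.4 | −1.3% | −5.8% | −10.2% |
| 0.6 | −2.8% | −11.8% | −19.4% |

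Middle case (R² = 0.4, r = 0.90): 0.600 / (1 − 0.4 × 0.81) = 0.600 / 0.676 = 0.888, and √0.888 = 0.942, so the interval is 5.8% narrower. This is worth 30 × 0.676 / 0.600 = 33.8 patients per group under the planned covariate. The difference detectable with 80% power falls from (1.960 + 0.842) × √(2 × 0.676 / 30) = 0.595 SD to (1.960 + 0.842) × √(2 × 0.600 / 30) = 0.560 SD.

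With assumed lognormal areas and 20% to 60% of patients having two or three ulcers, simulated r was about 0.92 to 0.98. That points to a gain of about 1% to 12% from total area alone.

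**3. Total area plus ulcer count (simulation).** Assumptions: 90 patients, lognormal ulcer areas, effort equal to a fixed part per ulcer plus a part per cm², and log-scale noise. The comparator covariate is log largest-ulcer area. CI width ratio is √(residual variance ratio).

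| Patients with 1/2/3/4 ulcers | Noise SD | Residual variance ratio | CI narrower by |
|---|---|---|---|
| 50/25/15/10% | 0.3 | 0.45 | 1 − √0.45 = 33% |
| 50/25/15/10% | 0.5 | 0.67 | 1 − √0.67 = 18% |
| 50/25/15/10% | 0.8 | 0.83 | 1 − √0.83 = 9% |
| 80/15/5/0% | 0.5 | 0.82 to 0.88 | 9% to 6% |
| 90/10/0/0% | 0.5 | 0.92 to 0.94 | 4% to 3% |
| 90/10/0/0% | 0.8 | – | about 1% to 1.5% |
| 100/0/0/0% | any | 1 | 0 |

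The 80% and 90% rows use a median area of 6 cm², log-SD 1, and a fixed part of 1, 5 or 10 per ulcer plus 1 per cm²; with these settings the 50/25/15/10% split at noise SD 0.5 gives 0.68 to 0.74. The range of about 1% to 10% for 10% to 20% multi-ulcer patients therefore holds for noise SD 0.5 to 0.8. With less noise the gain would be larger.

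**4. Cost of the extra covariate.** Two terms replace one. Counting each of the 11 covariates as one term, residual degrees of freedom go from 90 − 3 − 11 = 76 to 75. The variance penalty is about 76/75, or 1.3%, which is about 0.7% in CI width.

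**The case against.** **Whole-patient coverage is partly inferred.** The per-patient pricing supports it for cost. For time, the documents do not say outright that every ulcer is included, and the collection forms are in appendices not available here. This stands, so the point is firm for variable 7 and a natural reading for variable 8.

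**The size is assumed.** The number of ulcers per patient decides the effect and is not in the documents. The simulation also generates effort from the same two quantities proposed as covariates, which favours them, and a reduction in residual variance looks larger than the matching change in CI width. This stands too. The size should be read as CI width and over the full range from no multi-ulcer patients upwards.

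**Stronger readings are not supported.** A reader might infer that the cost and time comparisons are biased. They are not on this account: allocation is random, so ulcer burden differs between arms only by chance. A reader might also infer that ulcer burden is the main driver of cost and time. No figure shows that, and the plan names other drivers, such as the unlike materials and change schedules of the arms. Nor can it be said that total burden is recorded before randomisation. Section 3h places measurement at the first visit and randomisation straight after cleansing at that visit, without ordering the two, and ulcer count is derivable but not a named item.

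**Most of the information is kept.** Largest-ulcer area is strongly correlated with total area, so the loss is partial. Cost and time are two of 14 dependent variables, and research question 1 does not rest on them.

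**Conclusion.** The mismatch is real. A whole-patient outcome (cost, and time on the natural reading) is adjusted for the size of one ulcer, while measurements of all ulcers exist from the first visit. The consequence is a modest loss of precision and uncorrected chance imbalance. The gain from correcting it ranges from nothing, if every patient has one ulcer, to about a third of CI width in the most favourable assumed case; if only a minority have several ulcers it is more likely to be a few percent. The assumptions that matter are the share of patients with several ulcers, the noise in cost and time, and whether effort scales with both count and area. This is an optional refinement that does not affect the trial's validity.

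**What to change.** Add one sentence to section 3i: for variables 7 and 8, the ANCOVA size covariates are the log of the total area of all dressed ulcers and the number of ulcers, in place of independent variable 7. Take both from first-visit measurements only, and do not redefine them if ulcers later merge; this also keeps the covariates independent of events after allocation. Keep study-ulcer area as the covariate for the ulcer-level outcomes (variables 10 and 11). State in section 3d that variables 7 and 8 cover all dressed ulcers, if that is the intention.

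The cost is summing areas that are already measured, counting the ulcers, and one extra covariate degree of freedom. No new data collection is needed.
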